3.1.2 Secondary outcomes

- a) Proportion of women with postpartum depression, measured using the Edinburgh Postnatal Depression Scale at six weeks and six months postpartum.
- b) Change in mean postpartum hemoglobin levels at two weeks and six weeks postpartum.
- c) Achievement of a non-anemic state (Hb≥11.0g/dl) at six months postpartum.
- d) Prevalence of moderate/severe anemia at six weeks and six months postpartum. Moderate anemia is defined as hemoglobin level 7.0-9.9g/dl and severe anemia as hemoglobin level <7.0g/dl.
- e) Change in mean serum ferritin, serum transferrin, serum iron and % transferrin saturation at two weeks and six weeks postpartum.
- f) Need for blood transfusion after iron treatment during the first 6 weeks postpartum.
- g) Prevalence of fatigue at six weeks and six months postpartum, measured using the Fatigue Severity Scale (revised FSS-5R version) (22).
- h) Proportion of women with secondary postpartum hemorrhage after treatment. This will be defined as excessive bleeding requiring surgical intervention or blood transfusion from 24 hours after delivery till 12 weeks postpartum (23).
- i) Proportion of infants being breastfed (exclusive and any) at six weeks and six months postpartum.
- j) Prevalence of impaired maternal-infant bonding at six weeks and six months postpartum measured using the Mother-to-Infant Bonding Scale (MIBS) (20).
- k) Incidence confirmed or suspected maternal infection within 6 weeks of birth, as defined by a new prescription of antibiotics for presumed perineal wound-related infection, endometritis or uterine infection, urinary tract infection or other systemic infection (clinical sepsis).
- I) Incidence of hypophosphatemia at two weeks and six weeks postpartum. We will measure vitamin D, alkaline phosphatase, P1NP, FGF23, Ca, PO₄, which are biomarkers of phosphorus homeostasis and bone turnover. Hypophosphatemia is defined as serum phosphate level <2.5mg/dL (0.81mmol/L). Mild hypophosphatemia as 2-2.5 mg/dL (0.65-0.81 mmol/L), moderate as 1-2 mg/dL (0.32-0.65 mmol/L), and severe as <1 mg/dL (0.32 mmol/L).
- m) Incidence of early neonatal death, defined as death of newborn from enrolment of the mother to before seven completed days.
- n) Incidence of late neonatal death, defined as death of the newborn from enrolment of the mother to before 28 completed days.
- o) Incidence of infant death, defined as death from enrolment before the age of six months.

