- p) Incidence of post-natal maternal death from enrolment up to six weeks and at six months postpartum.
- q) Incidence of adverse drug events.
- r) Quality of life measured using the WHOQOL BREF at enrollment, six weeks, and six months post-partum.

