4.3 Sample size

We will enroll 1400 women into the trial. Power calculations assume a 1:1 randomization ratio to each of the two treatment groups.

For the primary outcome (anemia), we used data from a recent meta-analysis (28), which reported that 39% of women were anemic at six weeks postpartum. A sample size of 697 participants per arm would

^{**}A prospective participant with chronic medical condition (e.g HIV infection) will not be excluded unless there are contra-indication for the use of iron supplementation.

provide 90% power to detect to detect a relative reduction of 20% for IV iron to reduce the event rate of anemia at six weeks postpartum to 30%, after accounting for 10% loss to follow-up.

Bearing in mind the proposed one-time interim analysis to be conducted by the Data and Safety Monitoring Board (DSMB) at mid recruitment, we applied the O'Brien-Fleming rule (29), adjusting our final alpha level to 0.0492 (*See section 9.3 for interim rule*), which increased our final sample size to 1400 (700 per arm of the study).

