4.4 Randomization

Randomization and enrolment will occur between six and 48 hours after delivery and the initial post-delivery blood loss. Postpartum women during this window (6-48 hours postpartum) will be screened, enrolled, and randomized to one of the two treatments groups. Individual randomization and allocation concealment will be done with the use of a web-based randomization software known as 'Sealed envelope' in a 1:1 ratio in blocks stratified according to study site (Table 1). Screening, consenting, enrolment and randomization will be done by dedicated and trained study research nurses/midwives at each participating study site.

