4.8 Physical examination

Full physical examinations will be performed at baseline, and at each visit. Examination will include measurement of the patient's weight and blood pressure, body temperature. An abdominal palpation will be performed to ensure the uterus is well contracted in all women; a physical examination of the perineum will be performed at baseline to ensure any perineal trauma has been identified. A physical examination of the breasts/perineum/abdomen will be performed if clinically indicated during follow up visits.

Information about the physical examination must be entered into the patients' clinical case notes/files at the study sites. Significant findings such as abnormal swelling, skin lesions, signs of inflammation/infection that are present prior to receiving study medication must be included in the relevant medical history/current medical conditions in the source document and the electronic Case Report Forms (CRFs).

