4.10.2 Enrollment and randomization visit (Visit 1)

Enrollment (visit-1) will preferably take place during the same visit/time as the screening (visit-0) or very shortly after within 6-48 hours after delivery.

• Once the participant has been screened and determined to meet study eligibility criteria and complete the informed consent document,

The following additional steps will be taken:

1. Go to Sealed Envelope and randomize the participant into a study arm.

- The participant will be assigned a study ID which will be used to identify the participant throughout the study.
- Complete the enrollment log sheet (*Appendix vii*) with the participant's assigned study ID and treatment arm.
- The study ID only will also be written on her clinical case-notes (source document).

2. Go to REDCap

- Complete participant's biodata and locator form (Appendix viii): For each participant, the research nurse (RN) will obtain contact information, which will include the participant's phone number, her partner's phone number, her home address, major landmark to her home, occupation, and other necessary information as provided by the participant. The RN should determine the best way to collect this information for each study participant and complete it in the participant's biodata and locator form. If a participant misses a scheduled appointment (follow-up or end of study visit), the research staff will try to establish communication with the participant through authorized possible means (e.g., phone, emails or visiting the participant's home or workplace). The need to complete all scheduled follow up visits must be emphasized to all study participants at enrolment and at every visit.
- Take relevant medical history and concomitant medication information.
- Do a physical examination
- Evaluate for the presence of any symptom and sign (adverse event(s) AEs)) and if any,
 complete and submit the adverse event e-form (Appendix ix).
- **Complete enrollment e-CRF (***Appendix x***)** and relevant source document (SD) to document relevant baseline observation.
- Take blood samples for laboratory tests complete the blood sample collection log.
- Administer study drug (intervention or control) according to randomization and protocol for study drug administration (section 4.6.1)

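### Secondary outcome (k), maternal infection, opens its window at birth, so a prescription issued before randomisation can count as an event.

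*Protocol*

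**What the plan says.** Section 3.1.2 defines outcome (k) as "Incidence confirmed or suspected maternal infection within 6 weeks of birth, as defined by a new prescription of antibiotics". The prescription must be for a presumed perineal wound, uterine, urinary or other systemic infection. Birth is the only time anchor in the definition.

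Section 4.4 states: "Randomization and enrolment will occur between six and 48 hours after delivery and the initial post-delivery blood loss". The exclusion criteria in section 4.2.1 mention neither current infection nor current antibiotic treatment.

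Neighbouring outcomes in section 3.1.2 start at or after trial entry:

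- (m): "Incidence of early neonatal death, defined as death of newborn from enrolment of the mother to before seven completed days". Outcomes (n) and (o) also start at enrolment.
- (p): "Incidence of post-natal maternal death from enrolment up to six weeks and at six months postpartum".
- (f): "Need for blood transfusion after iron treatment during the first 6 weeks postpartum".

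The protocol also foresees infection at baseline. Section 4.8 requires that "signs of inflammation/infection that are present prior to receiving study medication must be included in the relevant medical history/current medical conditions", and section 4.10.2 lists "Take relevant medical history and concomitant medication information" among the enrolment steps. Neither section is linked to (k).

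**The concern.** A randomised comparison can be informative only about events that happen after randomisation. The window of (k) opens up to 48 hours before that point. A possible record is a woman prescribed antibiotics for suspected uterine infection 12 hours after birth, randomised at 40 hours, with no infection afterwards. On the literal wording she can be scored as an event in whichever arm she joins.

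Two things are at stake. The relative risk for (k) is diluted, and section 1.1 lists infection among the maternal consequences of postnatal anemia. The reported incidence would also mix infection after treatment with infection already being treated at entry. Finally, because *new* has no stated reference point, two people deriving the outcome could code the same woman differently.

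**Working it through.** **Time anchors side by side**

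| Outcome (section 3.1.2) | Window opens |
|---|---|
| (f) transfusion | after iron treatment |
| (k) maternal infection | birth |
| (m), (n), (o) newborn and infant death | enrolment |
| (p) maternal death | enrolment |

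The part of the (k) window before randomisation is 6 to 48 hours out of 42 × 24 = 1,008 hours, that is 6/1,008 = 0.6% to 48/1,008 = 4.8% of the time.

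**Effect on the comparison**

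The protocol gives no rate, effect size or power for (k), so there is no figure of its own to reproduce. Every rate below is an assumption. Let *q* be the share of women with a qualifying prescription before randomisation (equal in both arms on average, because of randomisation), *p* the post-randomisation risk on oral iron and *R* the true relative risk. Assume that *p* and *R* are the same for women with and without an earlier prescription.

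- Counted risk, oral arm: q + (1 − q)p
- Counted risk, intravenous arm: q + (1 − q)pR
- Counted risk difference: (1 − q)p(1 − R), so it shrinks only by the factor (1 − q)

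If R = 1, the two counted risks are equal, so the extra events create no spurious effect.

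With p = 10% and R = 0.75:

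- q = 0: 10.0% against 7.5%; relative risk 0.75; difference 2.50 points.
- q = 2%: 0.02 + 0.98 × 0.10 = 11.8% against 0.02 + 0.98 × 0.075 = 9.35%; relative risk 9.35/11.8 = 0.79; difference 2.45 points.
- q = 5%: 0.05 + 0.95 × 0.10 = 14.5% against 0.05 + 0.95 × 0.075 = 12.125%; relative risk 12.125/14.5 = 0.84; difference 2.375 points.

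**Effect on precision**

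For equal arms, the sample size needed for fixed power is proportional to [p₁(1 − p₁) + p₂(1 − p₂)]/(p₁ − p₂)², where p₁ and p₂ are the counted risks.

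- q = 0: (0.0900 + 0.0694)/0.025² = 255
- q = 2%: (0.1041 + 0.0848)/0.0245² = 315; ratio to q = 0 is 1.23
- q = 5%: (0.1240 + 0.1065)/0.02375² = 409; ratio 1.60

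**Range over other assumptions**

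Section 4.3 plans 700 women per arm with 10% loss, so 700 × 0.9 = 630 evaluable per arm. With R = 0.70 and a two-sided 5% test of two proportions:

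| Assumed p | Power, q = 0 | q = 2%: counted relative risk | q = 2%: power |
|---|---|---|---|
| 5% | 26% | 0.79 | 19% |
| 10% | 48% | 0.75 | 40% |
| 15% | 67% | 0.74 | 60% |

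At p = 10% and q = 1%, the relative risk moves from 0.70 to 0.73 and power from 48% to 44%.

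**The case against.** The strongest reply is that *new* can be taken to mean new since baseline, with the six-week phrase fixing only the end of the window. Related text leans that way. Section 4.8 puts infection signs present before study medication into the medical history. Section 6.6 documents other medication given after the start of study drug as concomitant medication. Section 7.1 counts a pre-existing condition as an adverse event only if it worsens. This reading is possible, so the earlier prescription *can* count; it cannot be said that it *must*. But the protocol states it nowhere, and none of these sections redefines (k).

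A second reply is that anchors vary across the outcomes. Outcome (h), secondary hemorrhage, is described as after treatment yet is defined from 24 hours after delivery. That is true, and it softens any charge that (k) breaks a uniform rule. Outcome (h) does at least state a post-treatment intent, which (k) does not.

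A third reply is that a date filter belongs in the analysis plan, which is not shown. Derivation detail does belong there. Here, however, the protocol itself states the window, and a later filter would have to depart from it.

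The points on size stand in full. No document figure supports any particular *q*. Prophylactic courses do not count, because the prescription must be for a presumed infection. The risk difference barely moves. Section 4.3 powers only the primary outcome, so a larger required sample for (k) has no planning consequence.

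**Conclusion.** The definition should be corrected. As worded, (k) can include prescriptions that precede randomisation, and it is out of line with (f) and (m) to (p). The consequence is attenuation of the relative risk and some loss of precision. At an assumed 10% post-randomisation risk and relative risk of 0.75, the counted value is 0.79 for q = 2% and 0.84 for q = 5%. The effect is probably modest, and it concerns one secondary outcome.

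A reader might infer more than the documents support:

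- **That one arm is favoured.** It is not. Pre-randomisation events are expected equally in both arms.
- **That the dilution is severe.** Taking q = 10% would give a counted relative risk of (0.10 + 0.90 × 0.075)/(0.10 + 0.90 × 0.10) = 0.1675/0.19 = 0.88. That places as large a risk in the first 6 to 48 hours as in the rest of the six weeks, which is implausibly high.
- **That the 12-hour and 40-hour record is typical.** The documents say nothing about how often it would occur.
- **That the main result is at risk.** The primary outcome is hemoglobin at six weeks and does not depend on (k).

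**What to change.** Reword 3.1.2(k) so that the event is a new antibiotic prescription for one of the listed infections, started after randomisation and up to six weeks postpartum. Add that a course already started before randomisation is recorded as baseline concomitant medication and does not count unless a new course is prescribed for a new infection.

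The cost is one sentence in the protocol and a matching date rule in the derivation. Table 3 already schedules concomitant medication at baseline and at every follow-up visit, so no visit or assessment is added. The one practical step is to make sure that the form captures antibiotic start dates precisely enough to place them before or after randomisation.

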1.1 Background

Anemia in pregnancy is a major public health burden with a high incidence in low- and middle-income countries (LMICs) such as Nigeria (1). It is most commonly caused by iron deficiency, which accounts for 50–75% (2). Postnatal anemia may result from untreated antenatal anemia or as a result of blood loss that occurs during birth. (3), and its prevalence in LMICs has been estimated to range from 50 to 80% (4). A study in Eastern Nigeria found anemia at 48 hours and six weeks postpartum to be 73% and 48% respectively, in a cohort of 202 women followed from late pregnancy until six weeks postpartum (5).

Anemia and iron deficiency anemia in pregnancy lead to increased morbidity and mortality for the mother and affects the neonates adversely (6). Specifically, postnatal anemia increases the risk of infection, leads to poor wound healing, and causes fatigue and depression in the mother (7). It also adversely affects breastfeeding, due to insufficient milk production, can reduce bonding between women and their newborn as a result of weakness and fatigue (3, 4, 8).

Oral iron is used routinely for the treatment of mild to moderate anemia in the postnatal period, while blood transfusion is offered for severe anemia or symptomatic women with moderate anemia (3). Oral iron, though inexpensive, causes significant gastrointestinal adverse effects such as vomiting, constipation, diarrhea, and abdominal pain (9), limiting adherence to this vital intervention which may pose a challenge in achieving optimum correction of anemia by the end of the postnatal period. Adherence to oral iron is reportedly low, with only 16% of women fully compliant with their treatment in a study among pregnant women in Cameroon, one of Nigeria's neighboring countries (10).

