4.2.1 Selection of participants

Inclusion criteria:

- a) Women aged between 15 and 49 years.
- b) Between six and 48 hours after delivery. A minimum of six hours has been chosen because we expect the initial post-birth blood loss to have subsided and the hemoglobin concentration to be sufficiently representative of the true hemoglobin concentration at that time; 48 hours has been chosen as the upper limit for pragmatic reasons because women are usually discharged from hospital after 48 hours.
- c) Baseline (enrollment) moderate or severe anemia (**Hb≤9.9g/dl**), confirmed by Hemocue haemoglobinometer.
- d) Able and willing to give written informed consent.

Exclusion criteria:

- a) Having received a blood transfusion, for any indication, within the last three months.
- b) Symptomatic anemia and a need for urgent correction.
- c) Known haemoglobinopathy such as sickle cell disease, HbCC disease.
- d) Clinically confirmed malabsorption syndrome.
- e) Known hypersensitivity or contraindication to any form of iron treatment, study drug or any of its excipients.
- f) Self-reported pre-existing maternal depression or other psychiatric illness and as evidenced by a YES response to Any Past history of Psychiatry ward hospitalization, Psychiatry medications, behavioral changes, or past consultation with Psychiatry services.
- g) Severe allergic conditions such as severe asthma, eczema, or other atopic condition.
- h) Known autoimmune conditions e.g., systemic lupus erythematosus, rheumatoid arthritis or known severe drug allergies.
- i) Planning to move or reside outside the research area
- i) Women who have had intravenous iron administered in the last two years (26).

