9.4 Data analysis plan

Primary analysis will be conducted by the intention to treat principle. Categorical variables will be expressed as frequencies and percentages. For continuous variables, a Shapiro-Wilk test of normality will be performed, and normally distributed data will be presented as means ± SD, while non-normally distributed data will be presented as median and interquartile range (IQR). However, the literature will be reviewed to ensure that variables are handled in their natural form. The effect of IV iron (vs. oral iron) on the primary endpoint (anemia at six weeks post-partum) would be analyzed using log-binomial regression models to obtain relative risks, 95% confidence intervals and p-values. The extent to which inclusion of baseline covariates modifies the precision of estimates would be explored. Generalized linear mixed models will be used to estimate the effect of treatment arm on repeated measures of hemoglobin and iron status biomarkers. The proportions of participants in the treatment arms who are anemic or iron deficient, and the proportions of participants who achieve anemia correction at 6 weeks and 6 months follow-up with be compared. Kaplan Meir plots and log-rank test will be used to explore the time to anemia correction. Subgroup analysis will be conducted to compare study findings by mode of delivery (caesarean vs vaginal delivery), and by the occurrence of primary post-partum hemorrhage. Two tailed test of hypothesis and 95% confidence interval is assumed as statistical level of significance. Stata version 17 (Stata Corp, Texas, USA) statistical software will be utilized for analysis. The variance estimator with cluster option (clustering on site of study) will be utilized.

Interim analysis will be conducted after achieving half of the sample size. Based on O'Brien-Fleming method (29), the threshold for significance of the primary endpoint at the interim analysis will be alpha = 0.0054. The clinical trial is terminated if the null hypothesis is rejected. The alpha level for the analysis at the end of the study will be adjusted to 0.0492 based on alpha adjustment based on O'Brien-Fleming method.

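### Secondary outcome (k), maternal infection, does not count a localized caesarean wound infection, although caesarean women are eligible

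*Protocol*

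**What the plan says.** Section 3.1.2 (k) announces "Incidence confirmed or suspected maternal infection within 6 weeks of birth" and then defines it by "a new prescription of antibiotics for presumed perineal wound-related infection, endometritis or uterine infection, urinary tract infection or other systemic infection (clinical sepsis". The definition makes these four items the scoring rule: perineal wound, uterus, urinary tract, and systemic infection.

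Four other places in the protocol bear on it:
- Section 4.2.1 admits women by age, hemoglobin and time since birth: "Between six and 48 hours after delivery". No inclusion or exclusion criterion refers to mode of delivery.
- Section 9.4: "Subgroup analysis will be conducted to compare study findings by mode of delivery (caesarean vs vaginal delivery".
- Section 1.1, in the rationale: "postnatal anemia increases the risk of infection, leads to poor wound healing".
- Section 4.8: "A physical examination of the breasts/perineum/abdomen will be performed if clinically indicated during follow up visits".

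On timing, (k) runs from birth, whereas section 4.4 places randomization 6 to 48 hours after delivery. The death outcomes (m) to (p) run from enrolment.

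**The concern.** The title of (k) promises all maternal infection and its definition delivers less. Caesarean women carry a wound that the definition does not name. Antibiotics prescribed for a localized infection of that wound do not meet the rule. They would count only if the infection became clinical sepsis or came with another listed infection such as endometritis.

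The rationale for treating postpartum anemia names both infection and wound healing, so the surgical wound is an obvious place to look for a benefit. As written, (k) cannot show one there. Site staff who meet such a case must leave it out or stretch the systemic category, and different sites may choose differently.

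A smaller point sits in the same sentence. Because the window opens at birth, an antibiotic started before allocation can be counted, although the allocated treatment cannot have influenced it.

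**Working it through.** **Text check.** The protocol states no figure for (k), so there is nothing to reproduce. Each kind of infection, treated with a new antibiotic prescription, is set against the list in 3.1.2 (k):

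| Infection | Counted by (k)? |
|---|---|
| Perineal wound | Yes, named |
| Endometritis or uterine | Yes, named |
| Urinary tract | Yes, named |
| Caesarean wound, with sepsis or endometritis | Yes, through those items |
| Caesarean wound, localized | No item fits |

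No other section shown widens the list.

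**Illustrative size.** The protocol gives neither the caesarean share nor any infection rate. All rates below are assumptions; only the trial size comes from the document (section 4.3: "We will enroll 1400 women into the trial").

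- c = caesarean share: 10%, 20%, 40%
- s = risk of a localized abdominal wound infection in caesarean women: 2%, 5%, 10%
- o = risk of a listed infection, in either delivery mode: 5%, 10%

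With the two risks independent, the full risk in caesarean women is t = 1 − (1 − s)(1 − o), and the scored risk is o. The share missed in caesarean women is (t − o)/t. The full overall risk is T = c·t + (1 − c)·o, and the share missed overall is (T − o)/T. The number of women missed is 1400 × c × (t − o).

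| c | s | o | t | Missed, caesarean | T | Missed, overall | Women of 1400 |
|---|---|---|---|---|---|---|---|
| 10% | 2% | 10% | 11.8% | 15% | 10.18% | 2% | 3 |
| 20% | 5% | 5% | 9.8% | 49% | 5.95% | 16% | 13 |
| 40% | 10% | 10% | 19.0% | 47% | 13.60% | 26% | 50 |
| 40% | 10% | 5% | 14.5% | 66% | 8.80% | 43% | 53 |

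Across the whole grid, 15-66% of infections are missed in caesarean women and 2-43% overall, which is about 3 to 53 women. In vaginal deliveries nothing of this kind is missed.

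**Power.** This uses a second set of assumptions: 630 per arm (700 less the protocol's 10% loss to follow-up), two-sided alpha 0.05, control rate of listed infections 6%, relative risk 0.7. The points added to the control rate are approximately the caesarean share (20-50%) times the wound infection risk (5-10%), so from 0.20 × 0.05 = 1.0 to 0.50 × 0.10 = 5.0 percentage points.

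| Definition | Control vs IV iron | Power |
|---|---|---|
| As written | 6.0% vs 4.2% | 31% |
| Plus 1.0 point, relative risk 0.7 for all | 7.0% vs 4.9% | 35% |
| Plus 5.0 points, relative risk 0.7 for all | 11.0% vs 7.7% | 52% |
| Plus 5.0 points, no effect of iron on these | 11.0% vs 9.2% | 18% |

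The last row takes 6.0 + 5.0 = 11.0 and 4.2 + 5.0 = 9.2. Whether power rises or falls depends on the effect assumed for the added events.

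**The case against.** **No bias between arms.** The same list applies to both arms and allocation is randomized, so the relative risk for the listed infections need not be distorted. A reader might infer that the trial's infection comparison is biased; the protocol does not support that.

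**The subgroup.** A reader might infer that the delivery-mode subgroup is invalidated. Section 9.4 speaks of study findings in general and does not name (k). A subgroup analysis also compares treatments within each mode and does not need equal raw rates across modes. What stands is that (k) is complete for vaginal deliveries and incomplete for caesarean ones.

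**Power.** A reader might infer that the wider definition brings more power. As the last table row shows, it can also lower it. Section 4.3 sizes the trial on anemia at six weeks, so no commitment for (k) is broken.

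**The data are partly there.** Section 7.2 records all adverse events from enrolment with the action taken, and section 6.6 and Table 3 record concomitant medication. A treated caesarean wound infection should appear there, so the events are lost to the endpoint rather than necessarily to the trial record. That does not alter the definition. At follow-up the abdomen is examined only when clinically indicated, so wound findings are not systematic.

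**The window.** Only the first 6 to 48 hours after birth are affected. Prescriptions in that time precede allocation and are balanced in expectation, so they add noise rather than bias. The word *new* might also be read as new since enrolment, though (k) gives it no anchor.

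An unseen analysis plan or e-CRF might capture these infections. The protocol nevertheless states a definition, and that definition leaves them out.

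**Conclusion.** The gap is real and follows from the text alone: a localized caesarean wound infection treated with antibiotics does not count as a maternal infection under 3.1.2 (k), although caesarean women can enter the trial and infection and wound healing are part of its rationale. The cost is lost events, no view of any treatment effect on caesarean wound infection, and an outcome that is incomplete for caesarean women.

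The size cannot be derived from the protocol. The 2-43% overall range rests wholly on assumed rates, and its width shows how little can be said about magnitude. The direction of any change in power is open.

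Severity is minor. This is one of 18 secondary outcomes, (a) to (r), and neither the primary outcome, the sample size nor the interim rule is touched.

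**What to change.** In 3.1.2 (k), replace the perineal item with *perineal or caesarean (abdominal surgical) wound-related infection*, and add the matching category to the follow-up e-CRF.

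In the same edit, count new antibiotic prescriptions from enrolment/randomization to six weeks postpartum, so that prescriptions before allocation do not enter. This brings (k) into line with the death outcomes, which already run from enrolment.

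The cost is a few words and one e-CRF category. Antibiotic use is already collected as concomitant medication. The change concerns outcome classification only and calls for no additional examination; since the abdomen is examined at follow-up only if clinically indicated, the category would rest on the recorded indication for the prescription.

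### Secondary outcome (n), labelled late neonatal death, has a window that contains all of the early neonatal window, so as written it measures total neonatal death after enrolment

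*Protocol*

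**What the plan says.** Section 3.1.2 of the protocol lists three consecutive infant mortality outcomes. The one at issue is the second of them, outcome (n): "Incidence of late neonatal death, defined as death of the newborn from enrolment of the mother to before 28 completed days". Directly above it in the list stands its early counterpart, outcome (m), which the protocol words this way: "Incidence of early neonatal death, defined as death of newborn from enrolment of the mother to before seven completed days". The third of the group, outcome (o), covers a longer period and is worded as follows: "Incidence of infant death, defined as death from enrolment before the age of six months".

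All three start at enrolment and differ only in where they end. Section 4.4 fixes that start: "Randomization and enrolment will occur between six and 48 hours after delivery and the initial post-delivery blood loss". No other section redefines late neonatal death, gives (n) a lower limit, or says whether the three outcomes are meant to be separate or cumulative. The data analysis plan in section 9.4 does not mention them.

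**The concern.** The words early and late form a pair that divides the neonatal period, so a reader expects (m) and (n) to be separate. As defined they are not. An infant who dies on day 3 counts in both.

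Three things follow:

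- The figure reported as late neonatal death is really neonatal death from enrolment onward. A reader who takes the label at face value gets a rate that is too high in either arm where a first-week death occurred.
- A reader who adds (m) and (n) to get total neonatal deaths counts the early ones twice.
- The label and the window give two different counts from the same data. One analyst may follow the window and another the label. In an open-label trial that choice is better settled before any results are seen.

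This is a fault in a definition that the protocol itself fixes. It is not a detail that a protocol would normally leave to the statistical analysis plan.

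**Working it through.** The protocol states no rate, event count or power for neonatal death, so it has no figure to reproduce. The check is a comparison of windows, followed by the algebra of the overstatement.

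**Inputs from the protocol**

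- Start of all three windows: enrolment, 6 to 48 hours after delivery (sections 3.1.2 and 4.4).
- End of (m): before 7 completed days.
- End of (n): before 28 completed days.
- Number enrolled, used only for illustration: "We will enroll 1400 women into the trial" (section 4.3), which is 700 per arm.

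**Step 1: compare the windows.**

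| Age at death | Meets (m) | Meets (n) |
|---|---|---|
| Enrolment to day 6 | yes | yes |
| Day 7 to day 27 | no | yes |
| Day 28 or later | no | no |

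No age meets (m) without meeting (n). Only days 7 to 27 belong to (n) alone.

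**Step 2: size of the overstatement if (n) is read as a late rate.** Let E be the deaths from enrolment to before day 7, and L the deaths from day 7 to before day 28. The count under (n) as written is E + L, while the count that fits the label is L. With s = E/(E + L):

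(E + L)/L = 1/(1 - s)

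The factor is 1 only if E = 0. If every death falls before day 7, the late count is zero and (n) is still positive.

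**Step 3: illustration.** The protocol does not give s, so these values are assumed:

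- s = 25%: 1/0.75 = 1.33
- s = 50%: 1/0.50 = 2
- s = 75%: 1/0.25 = 4

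In counts, assume also one infant per woman and a total neonatal death rate after enrolment of 10 to 30 per 1000, which is likewise not in the protocol:

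| Assumed rate | (n) as written, per arm | Days 7 to 27, s = 25% | s = 50% | s = 75% |
|---|---|---|---|---|
| 10 per 1000 | 700 × 0.010 = 7 | 5.25 | 3.5 | 1.75 |
| 20 per 1000 | 700 × 0.020 = 14 | 10.5 | 7 | 3.5 |
| 30 per 1000 | 700 × 0.030 = 21 | 15.75 | 10.5 | 5.25 |

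These rows show how the factor behaves and are not an estimate for this trial.

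**Step 4: after correction.** With late death limited to 7 to before 28 completed days, the overlap with (m) is empty, and early plus late deaths equal neonatal deaths from enrolment to before 28 days.

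**The case against.** The best defence is that the protocol uses a consistent cumulative scheme. Outcomes (m), (n) and (o) all run from enrolment over lengthening periods, and maternal death in (p) is also counted from enrolment to two horizons. On this reading the window of (n) is intended and only the word late is wrong. Several parts of this defence stand:

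- Under another name, the quantity in (n) is valid and compares the arms as randomized. A reader might infer that the between-arm comparison is invalid, but the text does not support that.
- Deaths from day 7 to before day 28 can be recovered as (n) minus (m) within each arm, if the definitions are published with the counts. A reader might infer that the trial's late rate could never be compared or pooled with others. That goes too far, since one subtraction restores it.
- No stated analysis adds (m) and (n) or combines them, so the overlap spoils no planned calculation.

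Two further inferences also lack support. A reader might attach a definite size to the overstatement, such as several-fold, but the protocol gives no neonatal death rate and no early share. Deaths before enrolment are not counted, so an early share taken from all births would not carry over directly. A reader might also argue that first-week deaths come too early for maternal iron to matter, but the protocol gives no time of onset for any effect on the infant.

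The defence does not rescue the text. If a cumulative outcome was intended, the label is wrong. If a late outcome was intended, the window is wrong. Outcome (o) does not have this problem, because the term infant death can include neonatal deaths, whereas late set beside early cannot include early ones.

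**Conclusion.** The point holds as an error in one outcome definition. Outcome (n) contains all of (m) and measures total neonatal death after enrolment. As a late rate it is overstated by 1/(1 - s) whenever an infant dies before day 7. The overlap follows from the protocol's wording alone and needs no assumption. The size cannot be determined from the protocol, and the factors of 1.33 to 4 shown above rest entirely on assumed early shares of 25% to 75%.

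The practical weight is small. This is one of 18 secondary outcomes, (a) to (r). The primary outcome, the sample size and the alpha levels do not depend on it.

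**What to change.** Amend section 3.1.2 (n) before analysis in one of two ways:

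1. Keep the window and rename the outcome neonatal death (enrolment to before 28 completed days). Report early deaths (before 7 completed days) and late deaths (7 to before 28 completed days) as non-overlapping parts.
2. Keep the label and define (n) as death from 7 to before 28 completed days.

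The first option keeps the cumulative scheme and needs only a change of name and a split in the table.

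With either option, state that the denominator for comparing the arms is all infants of randomized mothers alive at enrolment. Restricting it to infants alive at day 7 would condition on something that happens after randomization, so the groups compared would no longer be those randomized. A rate among day-7 survivors can be given for description only.

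The cost is one or two sentences. No new data are needed, because (m) already requires the infant's age at death, and no other part of the design changes.
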